Ver. 1.1

D.4.3. Tertiary Outcome: Changes in methylation at CpG sites of DNA

The tertiary outcome will be the assessment of methylation changes at “CpG” sites on DNA using a commercial available assay kit. CpG sites are sites on DNA in which a cytosine base is separated from a guanine base by only one phosphate; CpG sites are known sites for regulation by methylation. The Infinium MethylationEPIC Kit by Illumina uses the latest technology to assess methylation status of over 850,000 DNA sites across the genome. Using DNA provided from a saliva sample, this assay measured changes in methylation at “CpG” sites of DNA, i.e., whether or not sites for methylation are, or are not, methylated. For a given time point, the degree of methylation at each site (i.e., β) is presented as a color ranging from “green” (i.e., $\beta = 0$, low methylation) to “red” (i.e., $\beta = 1$, high methylation). We will compare the methylation state of participants at baseline to their status at the end of the study. “Differential” methylation is considered a change in CpG site methylation of $\Delta\beta \geq 0.66$. See Figure 2 below for a typical representation of the results of the assay.²⁸

Figure 2: Typical Demonstration of Results Applying the Infinium MethylationEPIC Kit

A saliva sample will collect approximately 2 mL (~1 teaspoon) into a cryovial. Saliva samples will be labeled only with a study ID, date of collection, and visit number and frozen to -70 °C.

At the conclusion of the study, all samples will be batched shipped to: Yale University Center for Genome Analysis Attn: [name], Associate Director of Microarray; [name].

D.4.4. Exploratory Outcomes: Changes in biomarkers associated with methylation

D.4.4.1. Methylation Profile – Doctor’s Data

Protocol

Study Title: Methylation Diet and Lifestyle (MDL) Study

PI: [name], ND, MPH and [name], ND

IRB #: RB100217

Approval Date: 2.9.18

Ver. 1.1

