Participants will be instructed to blend, shake, or briskly stir 1 level scoops of PhytoGanix into 8 ounces of water or juice two times daily. Participants will be instructed to take 2 capsules of UltraFlora intensive Care with 8 ounces of water once a day.

D.7.5. Product Adherence

Participants will be contacted by phone weekly Weeks 1-4 and semi-weekly Weeks 5-8 by the health coach team to check in on their progress. If participants report issues with product adherence product, the health coach team will discuss strategies with the participant to increase adherence. (For example, they may suggest posting note on the refrigerator or keeping the study product jar in a location such as a kitchen counter or dining table in order to incorporate taking the study product into daily routines.)

Adherence will be quantified by the study investigators who will count unused capsules and weigh unused study product after it is returned at the 5 week and 9 week study visits.

D.8. Blood and Saliva Collection and Analysis

Fasting blood samples and saliva samples will be obtained at the baseline, 5 week and 9 week visits. All study participants will be assigned a unique study ID number, and all blood samples, saliva samples, and laboratory paperwork will be identified with that number.

Blood collection will consist of a venous blood draw into of approximately 12 mL of blood (~2 tablespoons) into two EDTA (purple top) tubes and one finger stick collecting 5 drops of blood for a blood spot test.

These samples will be picked up by courier on the same day they are collected and transported to Doctor's Data, Inc for analysis.

Saliva sample collection will include approximately 2 mL collected from each participant. Participants will have abstained from food or beverages, except water, overnight prior to the collection. Participants will simply spit into a screw topped cryovial labeled with their study ID, date of collection, study time point, and approximate volume. If necessary, participants will be allowed up to 8 oz., of water in order to provide the sample, waiting at least 15 minutes between water intake and the sample collection. If necessary, cotton buccal cushions/swabs will be provided for participants to chew on to induce salivation.

E. HUMAN SUBJECTS RESEARCH

Protocol

Study Title: Methylation Diet and Lifestyle (MDL) Study

PI: [name], ND, MPH and [name], ND

IRB #: RB100217

Approval Date: 2.9.18

Ver. 1.1

E.1. Potential Risks

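### Chewing cotton to stimulate saliva for the methylation array is optional, need not be the same at Visits 1 and 3, and is not listed as recorded

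*Protocol*

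**What the plan says.** All of the following is in the protocol.

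- **Source of DNA (D.4.3):** "Using DNA provided from a saliva sample, this assay measured changes in methylation at “CpG” sites of DNA".
- **Timing (D.8):** "Fasting blood samples and saliva samples will be obtained at the baseline, 5 week and 9 week visits". Table 4 marks the array itself at Visits 1 and 3 only.
- **Collection (D.8):** "Participants will simply spit into a screw topped cryovial labeled with their study ID, date of collection, study time point, and approximate volume".
- **Two aids for a participant who has difficulty (D.8):** "If necessary, participants will be allowed up to 8 oz., of water in order to provide the sample", with a wait of at least 15 minutes before sampling; and "If necessary, cotton buccal cushions/swabs will be provided for participants to chew on to induce salivation".
- **Comparison (D.4.3):** "We will compare the methylation state of participants at baseline to their status at the end of the study". That sentence names no comparison between arms. The same section calls a site differentially methylated when beta changes by at least 0.66.
- **Records:** the label items in D.4.3 are study ID, date and visit number, and D.8 adds approximate volume. The visit lists in D.5.8 name a saliva sample without further detail. They also say that staff complete a case report form, whose content is not shown.

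**The concern.** Whether saliva was stimulated can differ between a participant's two array samples, and nothing in D.8 prevents that. Saliva contains more than one cell type, and cell types can differ in methylation at a given site. If chewing cotton changes their proportions, measured beta moves at every site where the cell types differ, although no cell has changed its methylation. In a before-after comparison that movement cannot be told apart from an effect of time or of the intervention.

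A comparison of changes between arms would protect against this only if switching were equally common, and in the same direction, in both arms. The trial is open with a wait-list control. Participants are randomized before Visit 1, and intervention supplements are handed out or returned at the visits where saliva is taken. Whoever judges that stimulation is needed may therefore know the arm.

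At stake is the interpretation of small methylation changes in the tertiary outcome. The hypothesis in B.3 is that methylation at inflammation-related sites will change, and it carries no threshold. An unrecorded procedure cannot be recovered at the analysis stage.

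**Working it through.** The plan gives no figure on this point to reproduce. The possible size can only be bounded under a simple model.

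**Model (assumed).** With two cell types A and B and a fraction p of type A, measured beta at a site is p × β_A + (1 − p) × β_B. If neither cell type changes but p does, then

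spurious change in beta = (change in p) × (β_A − β_B).

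**Inputs.** Neither factor is in the protocol. Assumed: a change in p of 0.10 to 0.30 and a beta difference between cell types of 0.3 to 0.8. From the protocol: the 0.66 threshold (D.4.3) and 40 evaluable participants (D.3.1).

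**Step 1: a participant whose procedure changes between Visits 1 and 3.**
- Low end: 0.10 × 0.3 = 0.03.
- High end: 0.30 × 0.8 = 0.24.
- More extreme inputs: 0.50 × 1.0 = 0.50.

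**Step 2: against the protocol's threshold.**
- Shift needed at a site where the cell types are wholly discordant: 0.66 / 1.0 = 0.66.
- Shift needed where they differ by 0.8: 0.66 / 0.8 = 0.825.
- The high end from step 1 is 0.24 / 0.66 = 36% of the threshold.

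So the artefact alone does not produce a differentially methylated site as the protocol defines it. It could do so only on top of a real change of at least 0.66 − 0.24 = 0.42.

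**Step 3: effect on an arm's mean.** If a share s of an arm switches in the same direction, the mean artefact is s × 0.24 at the high end.
- 20% in both arms: 0.20 × 0.24 = 0.048 within each arm, and 0 between arms.
- 30% in one arm and 10% in the other: 0.072 − 0.024 = 0.048 between arms. With about 20 evaluable per arm (40 / 2) this is 6 participants against 2.
- Switches in opposite directions within an arm offset each other in the mean and leave only added noise.

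The switching shares are illustrations. The protocol gives no indication of how often stimulation would be needed.

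**The case against.** The case against is substantial, and most of it limits the point without removing it.

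- **A reader might infer two specimen types, spit and swab.** The text does not support that. Spitting is the only collection named, and the cotton is there to stimulate saliva. Whether fluid is ever taken from the cotton is not stated. The point concerns stimulated against unstimulated saliva.
- **A reader might infer a rule that the procedure is chosen afresh at each visit.** No such rule is written. The protocol is silent on consistency, and that silence is what needs filling.
- **A reader might infer that the trial would report a sampling artefact as an epigenetic effect.** Under the 0.66 definition it would not do so from this cause alone (step 2). The risk is confined to analyses of smaller changes.
- **A reader might infer that the intervention itself (probiotic, drink powder, more vegetables) shifts oral cells in one arm.** Nothing in the protocol bears on this, and it is not part of the point.
- **The mechanism and both inputs come from outside the protocol.** This stands. The range shows what could happen and is not evidence that chewing changes the cell mix.
- **Both arms have the same tests, and D.8 does standardise fasting and the wait after water.** True. Equal testing protects a between-arm comparison, but D.4.3 names a before-after one.
- **Absence from the label does not prove that the procedure goes unrecorded.** Correct, since the case report form is not shown. What can be said is that no part of the protocol lists it.
- **Adjustment for cell fractions belongs in the statistical analysis plan.** Agreed. Its absence from the protocol is no finding.

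**Conclusion.** The point holds as a modest and inexpensive improvement to sample collection. D.8 leaves optional stimulation of saliva without a criterion, without a requirement of consistency at a participant's two array visits, and without a listed record, while D.4.3 relies on change within participants between those visits.

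The possible artefact is about 0.03 to 0.24 in beta for a participant who switches. It is smaller in an arm's mean and zero between arms if switching is balanced. These figures rest on three assumptions: that chewing changes the cell mix, that the shift in cell fraction is 0.10 to 0.30, and that the cell types differ by 0.3 to 0.8 in beta at the affected sites. The artefact could be confounded with small methylation changes but could not alone meet the 0.66 definition. The outcome is tertiary, in a trial that calls itself preliminary, and the primary PROMIS-29 analysis is not touched.

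It is still worth acting on, because the remedy has to be applied when the samples are collected.

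**What to change.** In D.8:

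- make unstimulated spit the default;
- require the same procedure, stimulated or not, at Visits 1 and 3 for each participant where a sample can be obtained;
- record on the case report form at each visit which procedure was used.

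For the methylation outcome, compare changes between arms as well as within them, and show the results with and without participants whose procedure changed.

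The cost is a sentence or two in D.8, one case report form field and one added sensitivity analysis. The downside is that some samples may take longer to give.

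Estimating cell fractions from the array data and adjusting for them is an optional further sensitivity analysis, and it may already be in the statistical analysis plan. It is also a choice of what to estimate, because adjustment would remove any true effect that acts through the cell mix.

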Understanding that environmental factors can potently and sometimes rapidly, favorably or negatively influence epigenetic expression, a short-term diet and lifestyle intervention may significantly augment DNA methylation expression.

The purpose of this study is to evaluate a 9-week diet and lifestyle intervention on patient-reported quality of life, symptoms, and DNA and biochemical methylation-related biomarkers in healthy males ages 50-72.

B. SPECIFIC AIMS

B.1 Primary Aim:

To evaluate a 9-week diet and lifestyle intervention on patient-reported quality of life.

Hypothesis: Quality of life will improve as a result a 9-week diet and lifestyle intervention, relative to a wait-list control condition.

Outcome measure: Changes in patient-reported quality of life, measured by the PROMIS-29 (Patient-Reported Outcomes Measurement Information System-29) questionnaire.

B.2 Secondary Aim:

To evaluate changes in patient-reported symptoms after a 9-week diet and lifestyle intervention.

Hypothesis: Severity of patient-reported symptoms will decrease following a 9-week diet and lifestyle intervention.

Outcome measures: Changes in patient-reported symptoms, measured by the MYMOP (Measure Yourself Medical Outcome Profile) questionnaire, NUNM Multi-system side effects/symptoms questionnaire, and the Medical Symptom Questionnaire (MSQ).

Protocol

Study Title: Methylation Diet and Lifestyle (MDL) Study

PI: [name], ND, MPH and [name], ND

IRB #: RB100217

Approval Date: 2.9.18

Ver. 1.1

B.3 Tertiary Aim:

To assess changes in methylation at CpG sites of DNA after a 9-week diet and lifestyle intervention.

Hypothesis: Methylation at CpG sites associated with chronic inflammation will change after the 9-week diet and lifestyle intervention.

Outcome measure: Number of CpG methylation sites, measured by the Infinium MethylationEPIC Kit (Illumina, Inc.)

B.4 Exploratory Aims:

To evaluate changes in biomarkers associated with methylation.

Outcome measures: Changes in the methylation related biomarkers as measured by Doctor's Data Methylation Index Panel, Methylation Profile, and Folate Vitamer Panel.

C. BACKGROUND AND SIGNIFICANCE

C.1. Methylation background and significance

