Inadequate diet and physical inactivity are indicated as two of the top 5 modifiable risk factors in several chronic diseases as well as associated with all-cause mortality.¹⁶ A diet lacking adequate intake of essential nutrients and antioxidants, as well as lack of exercise increase biomarkers associated with oxidative stress, endothelial dysfunction, and DNA hypomethylation.^{17,18} Oxidative overload places stress on cellular metabolic function, and is correlated with an increased risk of chronic diseases, such as cancer, cardiovascular and neurodegenerative diseases.¹⁹⁻²¹

With regard to the epigenome, poor diet has been associated with accelerated aging as evidenced by Horvath's Epigenetic Clock looking at DNA methylation patterns.⁸ Oxidative stress has also been shown to limit methyl donor availability, thereby impacting DNA methylation, by promoting transsulfuration and glutathione synthesis while inhibiting the methylation cycle. Oxidative damage to the epigenome further contributes to aberrant DNA methylation patterns.²²

A nutrient-rich diet and regular, moderate, aerobic exercise reduces oxidative stress, and risk of disease, by increasing antioxidants and activity of antioxidant enzymes, while also altering gene specific DNA methylation levels.^{7,23,24} Phytochemicals in various plant foods have demonstrated the ability to modulate DNA methylation. These include quercetin, found in red onion and apple skins, green tea, and red grapes; epigallocatechin-3-O-gallate (EGCG), found highest in green and white tea; genistein, found in soybeans; apigenin, found in parsley, artichoke, and celery; and curcumin, found in turmeric.²⁵ In addition, regular physical activity has shown to induce epigenetic changes in DNA methylation and lower homocysteine levels.^{26,27}

To date, this would be the first known clinical trial investigating diet and lifestyle intervention on patient-reported quality of life, symptoms, and DNA and biochemical methylation-related biomarkers in healthy males ages 50-72.

D. RESEARCH DESIGN AND METHODS STUDY FLOW

Protocol

Study Title: Methylation Diet and Lifestyle (MDL) Study

PI: [name], ND, MPH and [name], ND

IRB #: RB100217

[figure not shown]
Approval Date: 2.9.18

Ver. 1.1

D.1. Overview and Design

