
Choose organic at least half of the time.
 
Stay hydrated
 
Don't eat between 7pm and 7am, and at least 2 hours before bed
 
Include healthy oils
 
 • Balance types of fat • E.g. coconut, olive, flaxseed and pumpkin seed oil 
Avoid dairy, grains, legumes/beans
 
Minimize plastic food containers
	
3 cups colorful, low glycemic vegetables of your choosing
 
1-2 medium beet
 
4 tbsp (1/4 cup) pumpkin seeds (or pumpkin seed butter)
 
4 tbsp (1/4 cup) sunflower seeds (or sunflower seed butter)
 
1+ serving methylation adaptogens:
 
 • 1/2 cup berries (wild preferred) • 1/2 tsp rosemary • 1/2 tsp turmeric • 2 medium cloves garlic • 2 cups green tea (brewed 10 minutes) • 3 cups oolong tea (brewed 10 minutes) 
6 oz animal protein
 
 • grass-fed, pastured, organic and hormone/antibiotic-free 
2 servings of low glycemic fruit

These recommendations serve as a guidance, while individual intake may vary based on preference. Throughout the study, participants will be provided 2-week menu plans with recipes for all meals, snacks, smoothies.

Protocol

Study Title: Methylation Diet and Lifestyle (MDL) Study

PI: [name], ND, MPH and [name], ND

IRB #: RB100217

Approval Date: 2.9.18

Ver. 1.1

Refer to Appendix A for detailed nutrition recommendations.

D.2.2 Exercise Recommendations

Participants will be encouraged to exercise a minimum of 30 minutes at least 5 days per week at an intensity of 60-80% of maximum perceived exertion. Possible types of physical activity include, but not limited to, brisk walking, light jogging, hiking, dancing, yardwork, bicycling, and swimming.

D.2.3 Stress Management Recommendations

Participants will utilize the Cleveland Clinic's Stress Free Now application to engage in a variety of guided stress reduction techniques, including meditation and mindful breathing. Recommended frequency is twice daily, preferably morning and evening.

D.2.4. Lifestyle Recommendations

Participants are encouraged to average a minimum of 7 hours of sleep per night.

D.2.5. Study Supplements

Participants will be provided with two supplements. Details on the products are outlined in section D.12 of the protocol. Participants will take 2 servings of PhytoGanix and 2 capsules of UltraFlora Intensive Care probiotic daily, in divided doses.

D.2.6. Control group

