- The Principal/Clinical Investigator decided that withdrawal/discontinuation was in the best interest of the participant due to an adverse event, non-compliance, or another reason
- The participant requests withdrawal from the study for reasons other than above
- The participant failed to return for study visits

If a participant withdraws before the second visit, they will be replaced, however participants who withdraw between the second and third visits will not be replaced. Every effort will be made to collect a final salivary sample and all final labs from all participants, even if they withdraw from the study early.

D.7. Study Products

D.7.1. PhytoGanix (tropical fruit flavor)

Organic Superfruits & Greens Powder Drink Mix is a food-based phytonutrient blend designed to support intestinal health and immune function.

Protocol

Study Title: Methylation Diet and Lifestyle (MDL) Study

PI: [name], ND, MPH and [name], ND

IRB #: RB100217

Approval Date: 2.9.18

Ver. 1.1

Serving Size: 1 Scoop (10.4 grams)

Ingredient	Amount per serving
Calories	40
Total Carbohydrate	9 g
Dietary Fiber	1 g
Sugars	1 g
Protein	1 g
Vitamin C (as ascorbic acid)	100 mg
Calcium	20 mg
Iron	1.4 mg
Sodium	30 mg
Organic Seed and Prebiotic Blend:	5.53 g
Isomalto-Oligosaccharide, Flax Seed Powder, Chia Seed Powder, Quinoa (Chenopodium quinoa Willd.) Sprout Powder	
Organic Veggie Blend:	2.35 g
Spirulina Whole Algae Powder, Carrot Root Powder, Broccoli Head Powder, Cauliflower Head Powder, Spinach Leaf Powder, Parsley Leaf Powder, Bamboo Shoot Extract, Beet Root Powder	
Organic Fruit Blend:	1.2 g
Apple Fruit Powder, Pineapple Fruit Powder, Strawberry Fruit Powder, Raspberry Fruit Powder, Blackberry Fruit Powder, Blueberry Fruit Powder	
Herbal Support Blend:	300 mg
Milk Thistle Seed Extract, Turmeric Rhizome Extract, Green Tea Leaf Extract, Reishi Mushroom Whole Plant Powder, Maitake Mushroom Whole Plant Powder, Shiitake Mushroom Whole Plant Powder, Japanese Knotweed Root Extract, Quercetin Dihydrate, Organic Maca Root Powder, Organic Cassia Bark Powder, Dong Quai Root Powder, Ginger Root Powder, Garlic Bulb Powder	
Enzyme Blend (including protease, amylase, lipase, and cellulase)	200 mg
Lactobacillus acidophilus VK3 Strain	200 mg

Protocol

Study Title: Methylation Diet and Lifestyle (MDL) Study

PI: [name], ND, MPH and [name], ND

IRB #: RB100217

Approval Date: 2.9.18

Ver. 1.1

D.7.2. UltraFlora Intensive Care

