Probiotic designed to help maintain healthy flora and bowel function during dietary changes, promote the integrity of the GI intestinal barrier, and support a healthy immune response.

Ingredient	Amount per serving
Lactobacillus plantarum 299v Strain	20 billion live Strain organisms ^{††}

Ingredients: *Lactobacillus plantarum* 299v Strain, Potato starch, capsule (hydroxypropylmethylcellulose), *Lactobacillus plantarum* 299v (soy), and magnesium stearate (vegetable).

D.7.2. Product Descriptions

PhytoGanix contains organic fruit, vegetables, chia, quinoa sprouts, herbs, plant enzymes, prebiotics and probiotics. PhytoGanix Intensive will be provided and packed by Metagenics, Inc. in individual serving packets. It should be stored at room temperature in a cool, dry place.

UltraFlora Intensive Care contains the *L. plantarum* 299v strain of probiotics to help relieve intestinal irritation and bowel discomfort, promote the integrity of the GI intestinal barrier, and support a healthy immune response. UltraFlora Intensive Care will be provided and packed by Metagenics, Inc. in glass jars containing 30 capsules. It should be stored at room temperature in a cool, dry place or keep refrigerated.

The study products will be labeled with the following information: the product name, the study title, the IRB #, dosing information, the phone # of the Study Coordinator and Clinical Investigator.

D.7.3. Product Dispensing

Participants assigned to the intervention group will be given ~60 packets of PhytoGanix (adequate to provide 2 servings per day until Visit 2) and 2 bottles of UltraFlora Intensive Care at Study Visit 1. They will be instructed to wait to take the supplements until after the Introduction Webinar during the first week of the study. This will cover the approximately 56 dosages needed until Visit 2, plus extra dosages to allow for any loss of product. Participants will be provided with written instructions on taking the study product. At Visit 2, participants will return any unused study product in exchange for 2 additional bottles of each study product to cover the approximately 56 doses needed from Visit 2 until Visit 3. At Visit 3, participants will return any unused study product.

Protocol

Study Title: Methylation Diet and Lifestyle (MDL) Study
 PI: [name], ND, MPH and [name], ND
 IRB #: RB100217
 Approval Date: 2.9.18

Ver. 1.1

D.7.4. Product Administration

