E.3. Potential Benefit

Participants may not receive a direct benefit from their participation in this research. Participants may experience improved quality of life through adherence to the lifestyle recommendations included in the proposed intervention, however their composite effects are unknown. Participants may experience improved cardiovascular health through adherence to the physical activity and stress management recommendations in the proposed intervention.

F. Importance of Knowledge to be Gained

The proposed research will benefit society by producing proof-of-concept data on the efficacy of diet and lifestyle factors to alter epigenetic signaling after a short-term intervention. Demonstrating alterations in methylation sites in pathways with known associations with disease risk may lead to improvements in disease prevention initiatives and interventions toward the improved health of the public.

G. DATA COLLECTION, SOURCES AND ANALYSIS

G.1. Confidentiality and Data Security

Throughout the study, measures to ensure the privacy of information on study participants will be maintained. All study investigators and staff have been certified in human subjects research and have received training in HIPAA regulations. Participants and staff will be informed of the confidentiality of information and assured that data will be used only for statistical purposes and group analyses in which the individual cannot be identified. No data beyond what is stated in the Informed Consent will be sought without authorization from the participant. Information on illnesses and hospitalizations will not be sought from hospitals or doctors without a signed medical release from the subject. Conversely, no information on any individual will be released to anyone other than study personnel without a signed medical release from the participant, or where appropriate, the next of kin or a physician in case of a life threatening emergency to the subject. All study personnel will be instructed not to discuss any participants with persons other than study personnel.

Each participant will be assigned a unique alpha-numeric ID upon screening. All blood tubes, and associated paperwork will be marked using the unique ID to protect patient confidentiality. All data resulting from study visits will be collected on standardized case report forms (CRFs). Data will be transferred from CRFs to a secure REDCap database for data management. REDCap

Protocol

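### Section F credits diet and lifestyle factors with any effect, but the programme tested also includes two supplements that only the intervention arm takes

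*Protocol*

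**What the plan says.** The stated purpose, and the primary aim in B.1, is "to evaluate a 9-week diet and lifestyle intervention on patient-reported quality of life". The tertiary aim in B.3 is "To assess changes in methylation at CpG sites of DNA after a 9-week diet and lifestyle intervention". B.2 uses the same label for symptoms. None of the three aims or their hypotheses mentions a supplement. Section F states the expected gain as "proof-of-concept data on the efficacy of diet and lifestyle factors to alter epigenetic signaling after a short-term intervention".

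The intervention itself is set out in D.2. Diet (D.2.1), exercise (D.2.2), stress management (D.2.3) and sleep (D.2.4) are followed by a separate item, D.2.5: "Participants will be provided with two supplements". Dispensing is confined to one arm. D.7.3 says "Participants assigned to the intervention group will be given ~60 packets of PhytoGanix", together with the probiotic, and the visit lists in D.5.8 make the supplements conditional on being in that group. The controls are wait-listed (D.2, D.2.6), and no placebo or supplement is described for them.

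On activity, C.2 says "Phytochemicals in various plant foods have demonstrated the ability to modulate DNA methylation" and names quercetin, EGCG, genistein, apigenin and curcumin with their food sources. The herbal blend in PhytoGanix (D.7.1) begins "Milk Thistle Seed Extract, Turmeric Rhizome Extract, Green Tea Leaf Extract" and also lists quercetin dihydrate. The vegetable blend lists parsley leaf powder.

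**The concern.** The label used in the aims and in F is narrower than what is given. Other parts of the protocol treat the supplements as something distinct from diet and lifestyle. Eligibility (D.3.2) asks for willingness to take the drink and the probiotic in a different bullet from willingness to follow the programme. E.1.2 gives product ingestion its own risk paragraph. G.5 refers to interventional products supplied by the sponsor. Non-prescribed supplements are also an exclusion, are washed out for 3 weeks in the intervention arm, and are a category for withdrawal, so the protocol regards supplement use as something to be controlled.

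What is at stake is the sentence that the trial may write at the end. If quality of life, symptoms or methylation measures improve relative to wait-list, a report following F would credit diet and lifestyle factors. The supplements could have produced some of that difference, and nothing in the design would show whether they had.

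**Working it through.** **1. What differs between the arms.** Intervention: diet, exercise, stress management and sleep guidance, plus PhytoGanix, plus UltraFlora (D.2.1 to D.2.5, D.7.3). Control: the same testing, no programme, no product (D.2, D.2.6).

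**2. Whether the supplements could bear on the outcomes, by the protocol's own account.**

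| Agent credited in C.2 | A source named in C.2 | Listed for PhytoGanix in D.7.1 |
|---|---|---|
| Quercetin | red onion, apple skins, green tea, red grapes | quercetin dihydrate |
| EGCG | green tea | green tea leaf extract |
| Curcumin | turmeric | turmeric rhizome extract |
| Apigenin | parsley | parsley leaf powder |
| Genistein | soybeans | no match |

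Four of the five agents have a counterpart in PhytoGanix. For UltraFlora no methylation effect is claimed. The soy note in its ingredient list does not say that it supplies genistein. Its description does say that it helps to relieve bowel discomfort. The MSQ has a digestive domain and the NUNM questionnaire a gastrointestinal one, so an effect of that kind could register in the symptom outcomes.

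**3. Whether the two parts can be separated.** Let D indicate the diet and lifestyle guidance and S the supplements, and write the mean change in an outcome as b0 + b1·D + b2·S.

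- Control arm: D = 0, S = 0, mean b0.
- Intervention arm: D = 1, S = 1, mean b0 + b1 + b2.
- Difference: b1 + b2.

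D and S are the same column. With 24 participants per arm (D.1), the 48 × 3 design matrix (intercept, D, S) has rank 2. Only the sum b1 + b2 is estimable. The Group*Visit model in G.4 has a single group factor, so it inherits this at each visit. The comparison of baseline with end of study in D.4.3 does not help either, because everyone in the intervention arm is assigned both.

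For contrast, a 2 × 2 layout or a third arm gives rank 3, and the parts could then be estimated separately. The result does not depend on sample size. The planned 48 enrolled for 40 evaluable (D.3.1) plays no part in it, and a larger trial of the same shape would have the same limit.

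**The case against.** The strongest reply is that D.2 places the supplements openly under the study intervention. The diet and lifestyle intervention of the aims can then be read as shorthand for the whole package, and no aim asks for component effects. This largely stands. A reader might infer that the aims are unanswerable or that the design has failed. The documents do not support that: randomisation to programme or wait-list gives a valid package effect, and G.4 tests that contrast for PROMIS-29.

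Four further points deserve weight.

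- PhytoGanix is described as food-based, the diet itself offers turmeric and green tea, and C.2 discusses these agents as constituents of foods. The sponsor could fairly regard the powder as close to diet. But the protocol lists it apart from the diet in D.2 and in eligibility, so the shorthand is not self-evident.
- Quercetin, green tea and turmeric are 3 of 13 ingredients in a blend of 300 mg per serving (2 × 300 = 600 mg per day), with no individual amounts given. Activity at that quantity is therefore not shown. Neither is inactivity, and the protocol offers no ground for setting it aside.
- Calls, app monitoring and webinars might be counted as a rival cause. D.2.7 presents the app and calls as aids to adherence, and D.5.9 uses the webinars to deliver the content. They are part of how the programme is given.
- F is a general statement of significance and G.4 commits to no component claim. Even so, F assigns efficacy to diet and lifestyle factors, and that attribution is what the design cannot carry.

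Two other readings go too far. One is that a positive trial would report the wrong cause; what can be said is that the cause would be unsupported. The other is that the diet and lifestyle share lies between 0% and 100%. That is a statement of non-identifiability, not a magnitude, and it is not even a bound if component effects oppose each other.

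**Conclusion.** The programme-versus-wait-list effect is validly estimated. Attribution of that effect to diet and lifestyle alone, as F states and the labels in B.1 to B.3 suggest, is unsupported. The aliasing is complete and holds at any sample size, and the documents give no basis for a numerical split. The methylation argument applies to PhytoGanix, and so to the tertiary and exploratory outcomes and to F. For quality of life and symptoms the supplements are aliased in the same way, with the probiotic's described bowel effect the plainest route to the symptom scores. The conclusion assumes only that the supplements are dispensed as D.7.3 says and that the controls receive none. It does not assume that either product works. The defect is one of labelling and attribution, and it should be corrected because it decides what the trial may claim.

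**What to change.** In B.1 to B.3 and their hypotheses, and in F, name the intervention as the coached diet, lifestyle and supplement programme (PhytoGanix and UltraFlora Intensive Care) compared with wait-list. Add one sentence to F: any effect will be attributed to the combined programme only, not to diet and lifestyle alone. Arms, sample size, procedures and analysis are unchanged. The cost is a protocol wording amendment and a narrower headline claim.

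An extra arm is not needed for this. It would be justified only if component attribution were wanted, and it would cost precision. The protocol states no effect size, SD, alpha or power. Assuming two-sided alpha 0.05 and 80% power, the detectable difference in SD units is (1.96 + 0.84) × √(2/n). That is about 0.89 with 20 evaluable per arm, and about 1.10 with the same 40 spread over three arms (about 13 each).
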